*We will work closely with the staff of another research study being conducted at the VA that has similar eligibility criteria, resulting in dual-eligible patients. In order to avoid patients being enrolled in both studies, which could result in patient burden, both studies will work with a statistician to identify these dual-eligible patients and randomly assign them to one study only prior to patient outreach and recruitment. 75% of these dual-eligible patients will be allocated to our study and 25% will be allocated to the other study in accordance with both programs' statistical power needs. Since both studies are similar in scope (e.g., weight loss, increasing exercise), we do not anticipate patients enrolled in one study will receive greater health benefits than patients enrolled in the other study.

Gender of Subjects

Subjects of both genders are included in the study.

Age of Subjects

The minimum age of the subjects is 18 and the maximum age is 75.

Racial and Ethnic Origin

There are no enrollment restrictions based upon race or ethnic origin.

Inclusion Criteria

Inclusion criterion: Having at least one HbA1c result in the prediabetic range (5.7-6.5%) in the 2 years prior to the start date of the study wave. In order to communicate with CHWs, patients must also speak either English or Spanish.

Exclusion Criteria

A diagnosis of DM, based on ICD-9 and ICD-10 codes applied during ambulatory encounters in the 2 years prior to the study wave; treatment with DM medication other than metformin (e.g. insulin or oral agents); age greater than 75 years; or exclusion by patient's PCP due to contraindication for lifestyle intervention or CHW outreach.

Vulnerable Subjects

The protocol includes collecting data from BH and VA clinical providers whose participation is vital to the success of the study. There is no coercion to enroll these clinic staff subjects. All such subjects can opt out by notifying the study staff that they would no longer like to participate in the study. Alternatively, subjects can decide not to complete surveys.

As we will be surveying a large random sample of pre-diabetic patients, it is possible that some of the survey respondents will be pregnant, mentally disabled, economically or educationally disadvantaged. Their exclusion from possible participation would prevent us from accurately sampling the population at random.

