- *Maintenance*: After 6 months of intensive coaching, CHWs will transition to making monthly phone check-ins with patients for another 6 months to reinforce the knowledge and behaviors taught earlier.

Data Collection

Patient Data

As a pragmatic, population-based trial, we aim to understand the impact of our interventions on panels of patients in a real clinic environment and therefore will not collect any clinical data directly from patients. Instead we will rely on measurements taken during regular clinic visits and recorded in the EMR. We will access this clinical and administrative data for VA patients through the VA Informatics and Computing Infrastructure (VINCI), a secure, high performance interface with VA's Corporate Data Warehouse (CDW), and for BH patients from the NYC Health and Hospitals CDW. Relying on routinely collected clinical data does have its challenges. Patients in our cohort at baseline may not return to the clinic at appropriate intervals, and there may be incorrect information within the EMR limiting our ability to assess the impact of the interventions on all patients. Learning from our previous work, we will mitigate these challenges by updating the study registry regularly, and validating our data during Phase I of the study as we construct the pre-DM registries.

We will have the CHWs administer a survey (in person or by phone) of all intervention patients to assess patient activation and self-reported behaviors (diet and exercise habits). We will survey each wave's cohort of intervention patients twice: at baseline and at the end of their 1-year intervention phase. Surveys will include an MTA MetroCard worth \$11 to incentivize response. Non-responders will be mailed up to two reminders. A statement will be included with the survey outlining the number of times the survey will be conducted (two), the timeframe for the surveys (now, and one year from now).

Implementation Research

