To assess the overall effectiveness of the CHW intervention we will compare cumulative DM incidence rates and time to DM incidence (in addition to other outcomes: weight loss, obesity rate, and health care utilization) between the two study groups, using intention-to-treat and per protocol analyses. Time to DM incidence at 12-month follow-up of the intervention and control arms, aggregated across the 4 study waves, will be compared using Cox proportional hazard regression models. Chi-square analyses will be conducted to compare outcomes between the two groups for categorical variables (e.g. obesity rate, PAM stage) and t-tests will be conducted for continuous outcomes (e.g. weight change, PAM score). We will then conduct (generalized) linear mixed-effects modeling, which will (1) take into account the intra-cluster correlation coefficient (ICC) of patients within providers and teams, (2) analyze repeated measures at several time-points (baseline, midpoint, and post-intervention) simultaneously, (3) include team or patient level baseline covariates easily, if they are found to be unbalanced between two arms, and (4) deal with attrition problems and other missing data automatically. For categorical outcomes, such analyses will be implemented using SAS Proc GLIMMIX, while using SAS Proc MIXED for continuous outcomes.

We will use multilevel survival analysis to determine the effect of the intervention on time to DM, as patients are enrolled in waves and the time to DM incidence may be censored by the end of study. Specifically, we will fit Cox proportional hazard regression models with mixed effects to examine the hazard ratio between two groups, adjusting for important covariates and taking into account the correlation among patients within teams.

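### Patients can qualify on an HbA1c up to 24 months old with no test at wave start, so undiagnosed pre-wave DM can be counted as incident over 12 months; the plan specifies no use of the test's date

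*Combined protocol and SAP*

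**What the plan says.** All references are to the combined protocol and SAP.

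- **Entry** (Inclusion Criteria): "Having at least one HbA1c result in the prediabetic range (5.7-6.5%) in the 2 years prior to the start date of the study wave". One result is enough, and it need not be the latest.
- **Exclusion of DM** (Exclusion Criteria): "A diagnosis of DM, based on ICD-9 and ICD-10 codes applied during ambulatory encounters in the 2 years prior to the study wave", and "treatment with DM medication other than metformin (e.g. insulin or oral agents".
- **Baseline testing** (Data Collection, Patient Data): the study "will not collect any clinical data directly from patients" and relies on values recorded at routine visits. No HbA1c is tied to wave start.
- **Follow-up testing**: PCPs in both arms receive reminders to order A1C tests (Control Group; Intervention Group). In the intervention arm, CHWs also contact patients who are due for visits so that screenings are completed. Control teams receive reports of patients due for an HbA1c (both in the attrition and missing-data text).
- **Outcome window** (Analysis: Patient Clinical Outcomes and Health Behaviors): "Time to DM incidence at 12-month follow-up of the intervention and control arms, aggregated across the 4 study waves". The same section also says that "the time to DM incidence may be censored by the end of study".
- **Covariates** (same section): the Cox model adjusts for covariates judged important, which are not listed. The condition "if they are found to be unbalanced between two arms" belongs to the repeated-measures mixed models, not to the Cox model.

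The date of the qualifying HbA1c is not named as a time origin, a covariate, an interval-censoring input or the basis of a sensitivity analysis. The planned sensitivity analysis concerns missing outcomes.

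**The concern.** Take a patient whose only HbA1c was in range 23 months before the wave and who has not been tested since. The patient carries no DM code and no DM drug, so both exclusions are passed. The first follow-up test is then the first look in about two years. If it shows DM, the patient is an incident case in the 12-month comparison, even if the change came before any CHW contact.

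The look-back can be twice as long as the outcome window. Cases that coaching could not have prevented, if found equally often in both arms, pull the hazard ratio towards 1. If they are found more often in one arm, the bias could go either way. Incident DM is the outcome on which the trial is powered, so this bears on the main result.

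**Working it through.** **The plan's own figures.** The sample size reproduces: 72 x 3.5 x 4 = 1,008 per arm, and 2,100 x 0.8 x 0.6 = 1,008. The stated 80% power cannot be reproduced, because no hazard ratio, ICC or attrition rate is given.

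**Inputs.**
- From the plan: 15% DM incidence over 3 years (Statistical Power and Sample Size), a look-back of 0-24 months and a 12-month outcome.
- Assumed, because the documents do not give them: a constant hazard; test ages uniform over 0 to b years; no intervening test; a share u of pre-wave onsets still uncoded and untreated at wave start; all onsets detected during follow-up.

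**Step 1: hazard.** λ = -ln(0.85)/3 = 0.0542 per year. The 12-month incidence is 1 - exp(-0.0542) = 5.27%, or about 53 control events per 1,008. Under a hazard ratio of 0.70 it is 1 - exp(-0.70 x 0.0542) = 3.72%.

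**Step 2: pre-wave onset.** P(b) = 1 - (1 - exp(-bλ))/(bλ). This gives 1.34% for 0-6 months, 2.66% for 0-12 months and 5.23% for 0-24 months.

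**Step 3: share of counted cases that predate the wave.** Share = uP / [uP + (1 - uP) x 5.27%].

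| Test ages | u = 100% | u = 50% | u = 25% | u = 10% |
|---|---|---|---|---|
| 0-24 months | 51% | 34% | 20% | 9% |
| 0-12 months | 34% | 20% | 11% | 5% |
| 0-6 months | 20% | 11% | 6% | 2.5% |

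**Step 4: apparent effect when the true hazard ratio is 0.70** (ratio of 12-month cumulative incidence, pre-wave cases equal in both arms).
- 0-24 months, u = 100%: (5.23 + 0.9477 x 3.72) / (5.23 + 0.9477 x 5.27) = 8.75/10.22 = 0.86.
- 0-24 months, u = 25%: (1.31 + 0.9869 x 3.72) / (1.31 + 0.9869 x 5.27) = 4.98/6.51 = 0.765. Recognised cases are excluded at entry; taking them out of the cohort as well gives a 21% share and 0.767. Hence about 0.77.

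**Step 5: longer follow-up.** If follow-up ran to 36 months, which at most the earliest entrants could reach, the upper-end inputs give 5.23 / (5.23 + 0.9477 x 15) = 5.23/19.45 = 27%.

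**Step 6: power, for illustration.** Without clustering and at two-sided 0.05, 80% power over 12 months needs a hazard ratio of about 0.54 (Schoenfeld). With test ages over 0-24 months and pre-wave cases equal in both arms, power at that ratio falls to about 67% (u = 25%) or 43% (u = 100%).

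**The case against.** **HbA1c is not the only evidence of DM-free status.** This stands. The code and medication exclusions remove recognised DM, so the point is confined to onset that nobody has recorded. The source of the 15% matters too: the plan does not say how DM was ascertained in that cohort. If it was DM recorded in routine data, many pre-wave conversions at that rate would already be coded and excluded, and u would be small.

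**A reader might infer that half of all cases predate the wave.** The documents do not support that. The 51% requires every pre-wave conversion to be unrecognised, with test ages spread over the full 24 months.

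**A reader might infer that these cases cluster early, or fall equally in both arms.** Neither is shown. The timing of reminders relative to wave start is not given. Intervention patients are those who were reached and consented, and only they receive CHW prompts for screening, so detection could differ by arm. Simple dilution is therefore only one possibility.

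**A reader might say that the analysis ignores the test date.** That is too strong. The Cox covariates are unlisted, so the date is unspecified rather than ruled out. It is still not pre-specified.

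**Routine data are a declared pragmatic choice.** This is true, and the plan acknowledges irregular visits and record errors. It does not address the age of the qualifying test, and the remedy below adds no testing.

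**Conclusion.** The point holds for undiagnosed DM. Followed exactly, the plan would count DM that began unrecognised before the wave as incident, and it specifies no use of the test's date to limit or examine this.

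The size cannot be settled from the documents, which give neither the distribution of test ages nor the share unrecognised. Under a constant hazard, uniform test ages and full detection within 12 months, the scenarios run from about 2.5% to 51% of counted cases. The middle example is 20%, with a true 0.70 appearing as about 0.77; the upper end is 51% and 0.86. The share is lower if follow-up extends to end of study (about 27% at 36 months on the upper-end inputs), and the plan's two statements of the follow-up window need reconciling. The apparent ratios also assume equal detection by arm, which is not assured. The sponsor can narrow the test-age part of the range from registry dates.

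**What to change.** Keep the 2-year entry window and add the following to the analysis plan.

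1. **Main remedy.** Pre-specify a sensitivity analysis of time to DM limited to patients in both arms whose most recent pre-wave HbA1c is recent, with a cut-off fixed in advance between 6 and 12 months before wave start, and below the diabetic range. The plan must state the threshold it uses for that range, since it gives no laboratory definition of incident DM. On the table above with u = 25%, the share falls from 20% to 11% with a 12-month cut-off or 6% with a 6-month one. It is reduced, not removed.
2. **Covariates.** Always include the most recent pre-wave HbA1c value and the months since that test in the time-to-DM Cox model. This gains precision and adjusts for arm differences. It does not itself take pre-wave cases out of the count.
3. **Reporting.** Report, by arm, test age at wave start and time to first follow-up HbA1c, so that unequal detection can be seen.
4. **Secondary check only.** Leaving out DM found in the first 90 days could favour one arm if CHW prompts change when patients are tested. If it is used, read it alongside item 3.

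The cost is plan wording. The HbA1c values and dates come from the registry data already used for eligibility. The downside is fewer events, and so less precision, in the restricted analysis.

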- 4. Develop, implement and assess strategies to recruit, train, and integrate peer CHW health coaches within the PCMH model.

The 36-month intervention will be conducted using a staggered entry design across four, overlapping, 12-month waves to account for CHW caseload limits. This study will test a scalable model of peer health coaching to address the millions of patients at risk for DM, using low cost, culturally congruent personnel to promote prevention of DM in PCMH practice. If successful, our study team will work with VA's Central Office and NY City's Health and Hospital Corporation to translate the model for larger scale implementation.

Characteristics of the Research Population

Number of Subjects

All 12 PC teams at VA NY Harbor and all 4 PCMH teams at BH will be eligible to participate. In our VA PROVE study, 51/52 PCPs participated in the intervention, and we expect similar rates in this project. Eligible patients will be identified through the study's pre-DM registry, which will be based on the EMR and Corporate Data Warehouse (CDW) at each site. This methodology builds on our ongoing national, retrospective cohort study of predictors of DM among veterans with pre-DM back to 2008. Based on preliminary analysis of VA NYHHS data from 2010-2012, 62% of veterans enrolled in PC without DM, have had an HbA1c test in the previous two years.

In the intervention group, we anticipate contacting 2,100 randomly selected patients (1,050 at the VA* and 1,050 at BH) to ultimately enroll about 1,100 patients (550 at the VA and 550 at BH). This outreach sample reflects our assumption that 20% of patients will be unreachable and that 60% of those reached will enroll in the study. Another 1,100 patients attributed to control group providers will be randomly selected as the control group, in accordance with the waiver of HIPAA authorization. As detailed below, the control group will not participate in the CHW intervention. The total sample, including the intervention and control groups, will be about 2,200 patients. This amounts to approximately 265 patients (across intervention and control groups) per wave and per clinical site.

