Such vulnerable patient populations may be excluded from CHW outreach as instructed by primary care physicians. (i.e. patient will not receive a letter about services or CHW coaching intervention).

Methods & Procedures

Control Group

The control group will not have access to CHWs. They will experience usual care in their primary care clinics. PCPs in the control group will receive reminders from the study team to order A1C tests for their patients in their study, as this pragmatically collected data is necessary to evaluate the study's main outcome.

Intervention Group: (CHW Health Coaching Integrated into Team)

CHWs will provide the diabetes prevention intervention, described below, to a randomly selected subset of eligible patients per wave in the intervention teams at each hospital. CHWs and the researchers will provide regular updates to the primary care providers in the intervention group on these activities. As with PCPs in the control group, intervention group providers will receive reminders to order follow-up A1C tests for their patients enrolled in the study.

Choice of intervention strategies for each patient: We will have patients across the entire spectrum of motivation. Since we target the full population at risk, it will include highly motivated patients, highly resistant patients and a large group in between with varying degrees of motivation and activation. Our toolkit driven approach, which includes a wide range of strategies aligned with patient activation levels, will be based on the same framework used when [name] helped revise the VA-DOD smoking cessation guidelines from a referral-based approach to a population-based one. In the revised guidelines, the underlying principle guiding all treatment decisions – which applies equally well in this proposed study – was *all patients should be offered treatment in the most intensive setting they are willing to attend*. Similarly, all patients with pre-DM will be encouraged to use the most intensive DM prevention intervention that they are willing to attend.

CHW Reach: We anticipate that up to 40% of pre-DM subjects will participate in hospital-based programs (MOVE! at VA and Healthy Lifestyles at BH) and another 10-20% will participate in the community based Diabetes Prevention Program (e.g. at local YMCAs).

Community Health Worker (CHW) Coaches - Recruitment and Training

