provider has switched teams, newly enrolled patients attributed to this provider will enter the study in their provider's current study arm. For the intervention group, CHWs will contact patients when they are due for PC visits to ensure that they complete regular screenings as one of the toolkit strategies. Loss to follow-up of patients assigned to control teams is a concern, however we will address it through data reports provided to the control teams, which will include patients due for an HbA1c screening.

To limit bias due to contamination and missing values, we will assess the baseline characteristics of patients who switch teams or are removed from the panel or have incomplete repeated outcomes, and compare them with that of the other participants. The (generalized) linear mixed-effect models discussed earlier can deal with attribution problem and other missing data automatically, under the missing-at-random assumption. This model assumes that the missing information only depends on the observed information, which allows us to utilize all the observed information. To better understand the nature of our missing data and its mechanism; we will summarize the outcome variables by discontinuation status/reason in each arm. If the trajectories of the primary outcome variables from those with incomplete data are similar to those with complete information, the data may be missing at random; otherwise, it may be missing not at random. We will then conduct sensitivity analysis to assess the impact of missing not at random data on our analysis. The sensitivity analysis will test whether our primary statistical analysis remains credible if we investigate cases where those patients with incomplete data have outcomes that are unfavorable to the intervention arm of the study (e.g. those with incomplete outcome data in the control arm are less likely to develop DM, lose weight or have improved glycemic control or that those with incomplete outcome data in the intervention group are less likely to have lost weight or improved glycemic control but more likely to have developed DM). The sensitivity analysis will be conducted via multiple imputation using sequential modeling, applying a SAS macro.

Analysis: Intervention Implementation

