All primary care staff will be given information about the proposed research during regular staff meetings, email announcements and a study flyer and then asked to participate. Staff providing verbal consent to participate will be randomized (as part of their PACT team) to either work with a CHW or serve as controls. Staff who opt-out will not be randomized, although might still work on a team that is included in the study. For example, if one primary care provider in a team declines participation, the other providers and team members consent, the team will be randomized to a study arm. If that team is randomized to an intervention arm, the

CHW would only work with the patients of the consenting providers. We anticipate that we will be able to obtain sufficient numbers of staff consenting to participate, as in our previous panel management study only one PCP out of fifty-one declined, and a majority of staff reported that the interventions and CHW support were helpful. Lastly, as CHWs will be extending services and interventions that are a part of regular, evidence-based practice on behalf of patients' primary care physician, patients will not individually consent to receiving phone calls, mailings, or any other contact with the CHW. For surveys, which are research procedures specific to this study, consenting elements will be presented at the top of the survey. Primary care teams will pre-approve all lists of patients receiving interventions as well as approving the content of the CHW's intervention. Patients will have the right to opt out of receiving outreach at any time. All mail materials will include instructions on how to stop receiving mail from the CHW.

A waiver of authorization for both recruitment/identification purposes and for study procedures has been sought. We use the electronic medical record to generate a list of eligible participants, in order to approach them to screen for eligibility. Without the requested Waiver, screening could not be practically carried out and would adversely affect the scientific rigor of the study.

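### From wave 2 on, eligibility can rest on HbA1c tests and diabetes codes made after staff know their arm, and the analysis guards against this only in part

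*Combined protocol and SAP*

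**What the plan says.** Under Inclusion Criteria a patient qualifies by "Having at least one HbA1c result in the prediabetic range (5.7-6.5%) in the 2 years prior to the start date of the study wave". Under Exclusion Criteria a patient is removed by "A diagnosis of DM, based on ICD-9 and ICD-10 codes applied during ambulatory encounters in the 2 years prior to the study wave". Both windows are tied to the wave, not to the randomisation of teams.

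On timing, Study Design states that "The 36-month intervention will be conducted using a staggered entry design across four, overlapping, 12-month waves". No start dates and no randomisation date are given. On allocation, the recruitment and consent section says "Staff providing verbal consent to participate will be randomized (as part of their PACT team) to either work with a CHW or serve as controls", so staff know their arm. The attrition paragraph of the analysis section deals with providers who change teams: in later waves "newly enrolled patients attributed to this provider will enter the study" in the arm the provider then belongs to. The arm is thus settled before later-wave patients are identified.

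On data sources, Data Collection (Patient Data) says the trial will "rely on measurements taken during regular clinic visits and recorded in the EMR" and commits to "updating the study registry regularly".

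Contact with the providers differs by arm. In the intervention arm, "CHWs and the researchers will provide regular updates to the primary care providers in the intervention group on these activities", and CHW Intervention adds that these providers receive and review lists of their selected prediabetic patients. Control teams receive reports naming patients due for HbA1c (attrition paragraph). Providers in both arms are reminded to order HbA1c for patients in the study.

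**The concern.** In a cluster trial, randomisation protects the comparison only if the patients counted in each cluster are identified independently of the arm. Here the arm is known to the people who order HbA1c tests and enter diagnosis codes, and those two acts decide who is on the eligible list for a later wave. More testing in one arm would add patients who would otherwise have stayed untested, perhaps at milder risk. Earlier diabetes coding in one arm would remove patients close to conversion. Either would make the two lists differ before any coaching.

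Drawing patients at random from each list does not help if the lists themselves differ. Nor does intention-to-treat, which governs patients only after they have entered. Any such difference would pass into the diabetes hazard ratio and could not be told apart from a coaching effect.

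**Working it through.** **Inputs from the protocol.** 24-month look-back (Inclusion and Exclusion Criteria). Four 12-month waves in 36 months (Study Design). Caseload 72, 3.5 full-time CHWs, 2,100 contacts, 20% unreachable, 60% consenting, about 70% tested in two years, 3-year incidence 15%, eligible pools of 8,200 at Bellevue and 1,100 at the VA (Statistical Power and Sample Size). 1,050 contacts and about 550 controls per site (Number of Subjects). Cox comparison at 12 months (analysis section).

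**Assumptions of this review.** One randomisation at the start of wave 1, evenly spaced starts, exponential hazard, two-sided 5% test, no allowance for clustering.

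1. *The plan's own figure.* 72 × 3.5 × 4 = 1,008 per arm, and 2,100 × 0.80 × 0.60 = 1,008. Both reproduce. The 80% power cannot be checked because no effect size is stated. Each wave supplies 72 × 3.5 = 252 per arm, so waves 2 to 4 supply 756 of 1,008 (75%).

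2. *Share of the look-back after randomisation* = min(24, start month) / 24. Month 24 is the latest start that lets a 12-month wave finish within 36 months.

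| Last wave starts | Wave 1 | Wave 2 | Wave 3 | Wave 4 | Mean |
|---|---|---|---|---|---|
| Month 24 (0, 8, 16, 24) | 0% | 33% | 67% | 100% | 50% |
| Month 18 (0, 6, 12, 18) | 0% | 25% | 50% | 75% | 37.5% |

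3. *How far later waves need new patients.* VA: 1,050 + 550 = 1,600 against 1,100 eligible, or 145% (92% against the 1,730 with prediabetes in the VA preliminary data). Bellevue: 1,600 / 8,200 = 20%. On the 1,100 figure, later VA waves must re-invite decliners or take newly identified patients.

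4. *Base rate.* Hazard = −ln(0.85) / 3 = 0.0542 per year; 12-month risk = 1 − exp(−0.0542) = 5.27%.

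5. *Scenario with no true effect.* Half of one arm comes from a pool with relative hazard r. HR = 1 − 0.5 × (1 − r). With D expected events at 12 months, m = √(D/4) × |ln HR| and the rejection rate is Φ(m − 1.96) + Φ(−m − 1.96).

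| r | HR | D | Rejection rate (nominal 5%) |
|---|---|---|---|
| 0.90 | 0.95 | 104 | 5.8% |
| 0.80 | 0.90 | 101 | 8.3% |
| 0.60 | 0.80 | 96 | 19.4% |

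6. *Testing route, fully affected wave.* If testing in one arm rises from 70% to 80%, the added patients make up 0.10 / 0.80 = 12.5% of the pool, assuming the same yield of in-range results. If their risk is 30% to 50% lower, the pool's relative hazard is 1 − 0.125 × 0.3 = 0.96 to 1 − 0.125 × 0.5 = 0.94. In the intervention arm that is an HR of 0.94 to 0.96; in the control arm it inverts to 1.04 to 1.07.

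7. *Coding route, fully affected wave.* If 1% or 2% of one arm's pool, with an assumed 50% event risk, is coded early and removed: (5.27 − 0.5) / 0.99 / 5.27 = 0.91, or (5.27 − 1.0) / 0.98 / 5.27 = 0.83. At the 50% mean exposure of step 2, the pooled HR is about 0.96 or 0.91.

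The testing, risk and coding shifts in steps 5 to 7 are not in the protocol. They show scale only.

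**The case against.** The strongest objection concerns direction. A reader might infer that later intervention cohorts will look healthier, because intervention providers get lists and updates. The documents do not support that. The lists and updates concern patients already selected for outreach and prompt no test in others. Control teams get reports of patients due for HbA1c, and both arms get reminders. An extra testing prompt could as easily sit in the control arm.

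Three further points stand. First, the plan is not silent: it checks baseline balance, adds baseline covariates if they are unbalanced, and adjusts the mixed-effects Cox model for important covariates. A milder pool should show partly as lower baseline HbA1c. Second, it would be wrong to say that all patients in waves 2 to 4 qualify on post-randomisation data: on the assumed dates two thirds of wave 2's window and one third of wave 3's precede randomisation, and one earlier in-range result is enough. Third, the larger scenario figures ask a lot. An HR of 0.83 needs 2% of the pool to hold 1.0 / 5.27 = 19% of the risk, all coded early in one arm and none in the other.

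What this leaves open is how adequate the safeguard is. Baseline HbA1c is not named as a covariate, adjustment depends on a balance test, no check is made by wave, and the Cox comparison is aggregated over the four waves. The planned missing-data sensitivity analysis concerns missing outcomes, not differential entry.

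**Conclusion.** The concern holds as an unguarded opportunity for identification bias, not as a demonstrated bias. Rolling eligibility, unblinded staff and arms that carry forward are all in the text. They affect up to three of four waves, about 756 of 1,008 patients per arm, to a degree that rises with the wave number.

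The exposure percentages rest on assumed wave dates and on a single randomisation at the start of wave 1. The arm-switch rule and the recruitment text suggest one randomisation, but neither states it. If teams were randomised earlier, wave 1 is exposed too. The hazard ratios are scenarios. Modest pool differences raise the 12-month rejection rate only slightly (5.8% at HR 0.95), though the estimate would still be biased. The documents support no claim about direction. The changes should be made because they cost little and must be pre-specified to be credible.

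**What to change.** 1. State the dates of team randomisation and of each wave. Flag every patient by whether they already qualified on data dated before randomisation. Base the flag on an in-range result inside that patient's own window: such a patient meets the HbA1c criterion whatever is tested later.
2. Pre-specify two sensitivity analyses of the diabetes hazard ratio: one restricted to flagged patients, one to wave 1. The first closes the testing route but not the coding route, since a later code can still exclude a flagged patient. The second closes both if randomisation falls at or just before the wave 1 start.
3. Pre-specify baseline HbA1c and wave as covariates in the primary Cox model, whatever the balance tests show.
4. Report by arm and wave the share of the panel tested, the share in range, and the patients newly coded with diabetes since randomisation.

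Fixing the Bellevue eligible list before randomisation is feasible in numbers, but it would admit patients whose only in-range result is over two years old and would leave the coding exclusion rolling. It is not advised unless the eligibility window is rewritten to match.

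The cost is one registry flag, some tabulation and reduced precision in the restricted analyses. Wave 1 alone gives about 504 × 0.0527 = 27 events against 2,016 × 0.0527 = 106, so the standard error of the log hazard ratio, 2/√D, rises from about 0.19 to 0.39. With starts at months 0, 8, 16 and 24, wave 4 adds nobody to the flagged set. Both analyses are checks on consistency, not replacements for the primary result.
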